6. GENERAL ANALYSIS DEFINITIONS

6.1 TREATMENTS

It is planned that in total up to 80 healthy male subjects participate in this study.

In Part I 64 subjects are planned to be included, according to 8 sequential groups comprising 8 subjects per group. Within each dose group, 6 subjects will receive the active drug and 2 will receive placebo.

Two additional higher dose groups with BI 706321 40mg and 60mg (capsule) are considered and will only be dosed after approval of a substantial amendment.

In Part II 12 subjects are to be randomly allocated to one of 3 treatment sequences R-T1-T2, T1-T2-R or T2-R-T1. In addition, up to 4 replacement subjects may be included. There will be a washout period of at least 12 days between the treatments.

For details of dosage and formulation see Table 6.1:1 and [Table 6.1:2](#) below.

Table 6.1: 1 Labels for treatments for use in the CTR – Part I

Dose group	Sort order	Treatment	Short label
1, 2, 9	1	P*	Placebo, oral solution, po, qd
3-8, 11	2	R*	Placebo, capsule, qd
1	3	A	BI 706321, oral solution, 0.3 mg, qd
9	4	I	BI 706321, oral solution, 0.6 mg, qd
2	5	B	BI 706321, oral solution, 1.2 mg, qd
11	6	K	BI 706321, capsule, 2*1 mg, qd
3	7	C	BI 706321, capsule, 4*1 mg, qd
4	8	D	BI 706321, capsule, 8*1 mg, qd
5	9	E	BI 706321, capsule, 3*5 mg, qd
6	10	F	BI 706321, capsule, 5*5 mg, qd
7**	11	G	BI 706321, capsule, 2*20 mg, qd
8**	12	H	BI 706321, capsule, 3*20 mg, qd

*: The placebo group in the safety evaluation will consist of all placebo treated subjects, regardless of the dose group in which they were treated, but separated by pharmaceutical formulation (capsule and oral solution).

**: Dose groups 40 mg and 60 mg will only be dosed after approval of a substantial amendment.

Table 6.1: 2 Labels for treatments for use in the CTR – Part II

Treatment		Short label	Test/Reference
X	BI 706321, tablet, 2*2mg, qd, fasted	BI tab fasted	T1
Y	BI 706321, tablet, 2*2mg, qd, fed	BI tab fed	T2
Z	BI 706321, capsule, 4*1mg, qd, fasted	BI cap fasted	R

The following separate study phases will be defined for the analyses of AEs:

Part I:

- **Screening** (ranging from 0:00h (midnight) on day of informed consent until first administration time of study drug (BI 706321 or Placebo))
- **On treatment**

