 - **BI/Placebo treatment** (separately for each treatment, ranging from the time of administration of BI 706321/Placebo until 0.00 h (midnight) on the day after trial completion date (planned 15-22 days after administration of BI 706321/Placebo))

Part II:

- **Screening** (ranging from 0:00h (midnight) on day of informed consent until first administration time of study drug in first study period (BI 706321))
- **On treatment**
 - **BI treatment** (labelled ‘BI tab fasted’, ‘BI tab fed’, ‘BI cap fasted’) (separately for each treatment, ranging from the time of first administration of BI 706321 in each period until next administration or 0.00 h (midnight) on the day after trial completion date, whatever occurs first)

Please note that all AEs reported between start of trial drug administration until end of individual's trial or until starting next treatment period will be considered on-treatment. Hence, on-treatment is defined until at least 15 days (Part I) and at least 8 days (Part II) after first treatment administration.

The following AE displays will be provided in the report:

Section 15.3 and Appendix 16.1.13.1.8 (for ClinicalTrials.gov and EudraCT) of the CTR displays:

In these displays, the on treatment phase will be analysed (labelled with the name of the study treatment (short label)). Screening will not be included in this analysis.

In section 15.3, the following totals will be provided in addition:

- a total over all BI treated phases ("BI Total") – Part I only
- a total over all placebo treated phases ("Plc Total") – Part I only
- a total over all on treatment phases included in this analysis ("Total")

In outputs for ClinicalTrials.gov and EudraCT both study parts will be combined in one table and the following totals will be provided:

- a total over all BI treated phases of Part I ("BI Total Part I")
- a total over all placebo treated phases ("Plc Total")
- a total over all on treatment phases of Part I ("Total Part I")
- a total over all BI treated phases of Part II ("BI Total Part II")
- a total over all on treatment phases included in this analysis ("Total")

In Section 15.4 and Appendix 16.2.7 (Listings) of the CTR displays screening will be included and no totals will be provided.

Tables of vital signs, ECG and laboratory values will present results by the above mentioned on treatment phase.

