For detailed information on the handling of the treatments refer to Technical TSAP ADS (analysis data set) plan and Analysis Data Reviewers guide.

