7. PLANNED ANALYSIS

The placebo group in the safety evaluation will consist of all placebo treated subjects, regardless of the dose group in which they were treated but separated by pharmaceutical formulation (capsule and oral solution).

Trial Parts will be reported separately if not otherwise stated.

Safety analysis (refer to [Section 7.8](#)) will be performed by [REDACTED] and will be presented in Sections 15.1 to 15.4 of the CTR and in Appendix 16.2 and 16.1.13.1.

Inferential statistical analyses of PK endpoints (refer to Section [7.5.2](#)) will also be performed by [REDACTED] and will be presented in Section 15.5 of the CTR and in Appendix 16.1.13.3.

Descriptive data analysis of PK [REDACTED] parameters and concentrations will be performed by the department [REDACTED] at [REDACTED] and will be presented in Sections 15.6 and 15.7 of the CTR and in Appendices 16.1.13.5 and 16.1.13.6.

The format of the listings and tables will follow the standards defined in the BI corporate guideline “Reporting of Clinical Trials and Project Summaries” [001-MCG-159] ([6](#)) with the exception of those generated for PK-calculations.

The individual values of all subjects will be listed, sorted by treatment group (Part I) / treatment sequence (Part II), subject number, and visit and actual treatment (Part II). The listings will be included in Appendix 16.2 of the CTR.

For end-of-text tables, the set of summary statistics for non-PK parameters is:

N	number non-missing observations
Mean	arithmetic mean
SD	standard deviation
Min	minimum
Median	median
Max	maximum

For analyte concentrations, the following descriptive statistics will additionally be calculated:

CV	arithmetic coefficient of variation
gMean	geometric mean
gCV	geometric coefficient of variation

For PK parameters, the following descriptive statistics will additionally be calculated:

CV	arithmetic coefficient of variation
gMean	geometric mean
gCV	geometric coefficient of variation

P10	10th percentile
Q1	1st quartile
Q3	3rd quartile
P90	90th percentile

The data format for descriptive statistics of concentrations will be identical with the data format of the respective concentrations. The descriptive statistics of PK parameters will be calculated using the individual values with the number of decimal places as provided by the evaluation program. Then the individual values as well as the descriptive statistics will be reported with three significant digits in the CTR.

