Tabulations of frequencies for categorical data will include all possible categories and will display the number of observations in a category, as well as the percentage (%) for each treatment group. Percentages will be rounded to one decimal place and will be based on all subjects in the respective subject set whether they have non-missing values or not. The category 'missing' will be displayed only if there are actually missing values.

Units of variables should be given in the titles or column/row descriptors in square brackets (e.g. [mg]).

Exclusion of PK parameters

The ADS ADPP (PK parameters) contains column variables APEXC and APEXCO indicating inclusion/exclusion (APEXC) of a PK parameter and an analysis flag comment (APEXCO). All analyses based on the PKS will include parameters if they are not flagged for exclusion, that is APEXC is equal to "Included".

Exclusion of PK concentrations

The ADS ADPC (PK concentrations per time-point or per time-interval) contains column variables ACEXC or ACEXCO indicating inclusion/exclusion (ACEXC) of a concentration and an analysis flag comment (ACEXCO). Exclusion of a concentration depends on the analysis flag comment ACEXCO. For example, if ACEXCO is set to 'ALL CALC', the value will be excluded for all types of analyses based on concentrations. If ACEXCO is set to 'DESC STATS', the value will be excluded from descriptive evaluations per planned time point/time interval. If ACEXCO contains the addition 'TIME VIOLATION' or 'TIME DEVIATION', the value can be used for further analyses based on actual times. If ACEXCO is set to 'HALF LIFE', the value will be excluded from half-life calculation (and, as a consequence, any calculation that relies on λ_z) only; the value is included for all other analyses.

Further details are given in 001-MCS-30-476 "TMCP Data Analysis" ([5](#)).

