7.8.2 Laboratory data

The analyses of laboratory data will be descriptive in nature and will be based on BI standards [001-MCG-157] [\(9\)](#).

Laboratory data will be analysed qualitatively via comparison of laboratory data to their reference ranges. Values outside the reference range as well as values defined as possible clinically significant will be flagged in the data listings.

It is the investigator's responsibility to decide whether a lab value is clinically significant abnormal or not (at the RPM/DBLM at the latest).

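### Does the SAP's split of the Part I placebo group by formulation need changing, given that the protocol pools it?

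*SAP*

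**What the plan says.** Protocol Section 3.2 states that, for analysis, the placebo control consists of every placebo subject from every dose group. Section 7.3.4 repeats this for the safety evaluation and compares the active groups with that single group descriptively. It allows the SAP to define further analysing treatments in addition. It also leaves the Part I central ECG endpoints and their analyses to the SAP.

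SAP Section 6.1 has two placebo labels in Table 6.1:1: P (oral solution; dose groups 1, 2, 9) and R (capsule; dose groups 3-8 and 11). The footnote pools placebo subjects "regardless of the dose group in which they were treated, but separated by pharmaceutical formulation (capsule and oral solution"). SAP Section 7 says the same for the safety evaluation as a whole: "regardless of the dose group in which they were treated but separated by pharmaceutical formulation (capsule and oral solution"). SAP Section 4 reports no change from the protocol.

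On totals, SAP Section 6.1 introduces Plc Total for adverse events with "In section 15.3, the following totals will be provided in addition", and names it again for the registry outputs. Section 7.8.4 uses it in the exposure-response model, which under Section 6.3 is run only if relevant ECG findings appear. For the other safety data, Section 6.1 says: "Tables of vital signs, ECG and laboratory values will present results by the above mentioned on treatment phase". That phase is defined separately for each treatment, so P and R stay apart. Section 6.1 then points elsewhere: "For detailed information on the handling of the treatments refer to Technical TSAP ADS (analysis data set) plan".

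**The concern.** The protocol names a comparator and the SAP describes another one. The section meant to list such departures is silent, and the permission to define analysing treatments reads as permission to add columns, not to replace the control group. The SAP names Plc Total where it wants it, so its absence from the vital-sign, ECG and laboratory tables looks like an omission.

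If those tables carry only the two formulation columns, each active group of 6 is read against 6 or 10 placebo subjects instead of 16. With groups this small, one outlying placebo subject weighs more. These tables matter because safety and tolerability are a main Part I objective, and Section 2.2.2.1 of the protocol assesses them partly through laboratory tests, ECG and vital signs.

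**Working it through.** **Counts.** Inputs from SAP Section 6.1: 8 dose groups of 8, each with 6 active and 2 placebo. Solution groups are 1, 9 and 2; capsule groups are 11, 3, 4, 5 and 6.

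- Planned Part I total: (3 + 5) × 8 = 64, which is the plan's own figure.
- Solution placebo: 3 × 2 = 6. Capsule placebo: 5 × 2 = 10. Pooled: 16.
- Dose groups 7 and 8 lie outside the 64, and protocol Section 1.2.3 says higher doses than 25 mg were not tested.

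**Precision, as an illustration only.** Assume equal variance and no formulation effect. The standard error of a difference in mean change against 6 active subjects, in SD units, is √(1/6 + 1/n):

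| Placebo group | n | Standard error | Ratio to pooled |
|---|---|---|---|
| Pooled | 16 | √(1/6 + 1/16) = 0.479 | 1 |
| Capsule | 10 | √(1/6 + 1/10) = 0.516 | 1.08 |
| Solution | 6 | √(1/6 + 1/6) = 0.577 | 1.21 |

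The 8% applies to the five capsule doses and the 21% to the three lowest doses. Neither applies at 34 h (central ECG and vital signs) or to the 48 h central ECG. There only dose groups 3-6 contribute, so placebo n = 4 × 2 = 8 with or without the split. For laboratory data no such figure arises, because SAP Section 7.8.2 names no mean: "Laboratory data will be analysed qualitatively via comparison of laboratory data to their reference ranges".

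**Frequency tables.** SAP Section 7 says these "will display the number of observations in a category, as well as the percentage (%) for each treatment group". One placebo subject with an ECG finding would show as 1/6 = 16.7% or 1/10 = 10.0%, against 1/16 = 6.3% pooled. The count is printed beside the percentage, so the pooled figure follows at once.

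**What can be recovered from the two columns.** SAP Section 7 fixes the statistics ("For end-of-text tables, the set of summary statistics for non-PK parameters is": N, mean, SD, minimum, median, maximum). Write m₁, s₁ for solution and m₂, s₂ for capsule. With all subjects observed:

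- Pooled mean = (6m₁ + 10m₂)/16.
- Pooled SD² = [5s₁² + 9s₂² + 3.75(m₁ − m₂)²]/15, where 3.75 = 6 × 10/16.
- Minimum, maximum and counts combine directly.
- The median does not combine from summaries. It can be computed from the listings: SAP Section 7 lists every subject's individual values in Appendix 16.2 by treatment group, and Section 7.8.4 repeats this for all quantitative ECG endpoints.

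**Where the pooled control is kept.** The Part I primary endpoint is the percentage of subjects with drug-related adverse events. It is displayed in report Section 15.3, where Plc Total is specified. The registry outputs and the exposure-response model also keep it.

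**The case for a change.** The strongest case for a change is about consistency. The protocol specified pooling although both placebo products were already in the plan (Section 4.1.1), so the split is a departure, and SAP Section 4 should have said so. No document outside the SAP cures that silence. One extra column in three table families and one sentence would cost almost nothing.

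The mismatch and the missing record stand. The consequence drawn from them is weaker, for four reasons.

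- Whether the tables will lack a pooled column is not known. Treatment handling is referred to a technical plan, and laboratory displays and table formats to sponsor standards. SAP Section 9, cited for ECG detail, is not in the public text. Only the silence of that text is established.
- For ECG, the protocol hands the analyses to the SAP. This does not cancel the general definition in Section 3.2, but it makes it hard to call the ECG columns unauthorised.
- The split has a rationale. The solution placebo is the tartaric acid solvent and the capsule placebo is microcrystalline cellulose. Dosing was sequential with the solution groups first, and Section 3.2 of the protocol admits possible time-related effects, expected to be small. Formulation-matched placebo subjects are therefore also nearer in time to their active groups.
- The 8% and 21% assume no formulation effect, which is the condition under which pooling is harmless. They also describe a comparison that neither document plans to calculate.

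**Conclusion.** No change to the plan is needed. The SAP describes a finer layout of the placebo data than the protocol does, and Section 4 should ideally have noted it. That is a gap in documentation. Following the SAP as written still gives sound descriptive safety results, because all 16 planned placebo subjects are retained and every pooled statistic, including the median, can be obtained from the planned tables and listings.

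No test, decision rule or primary-endpoint display depends on the split. Protocol Section 7.2 tests no hypotheses in Part I, and the non-PK summary statistics in SAP Section 7 contain neither a standard error nor a difference from placebo. The most that could be said is an 8% or 21% larger standard error for an unplanned contrast, under equal variance and no formulation effect. Against that, the split gives a comparator matched on formulation and closer in time.

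The conclusion rests on planned numbers (2 placebo subjects in each of 8 groups) and on the individual listings being produced as SAP Section 7 describes. It makes no claim about documents that are not public. An analyst who wants the pooled column in the vital-sign, ECG or laboratory tables can add it without new data and without altering any finding.

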7.1 DEMOGRAPHIC AND OTHER BASELINE CHARACTERISTICS

Only descriptive statistics are planned for this section of the report, based on the TS.

For trial part I, the data will be summarised by treatment group and in total.

For trial part II, the data will be summarised by treatment sequence and in total.

7.2 CONCOMITANT DISEASES AND MEDICATION

Frequency tables are planned for this section of the report, based on the TS.

Concomitant diseases will be coded using the latest version of the coding system of the Medical Dictionary for Drug Regulatory Activities (MedDRA). Medications will be coded using the latest version of the World Health Organization Drug Dictionary (WHO-DD). The coding version number will be displayed as a footnote in the respective output.

The diagnoses and medications will be listed. Subjects without any concomitant diagnoses or concomitant therapies should be marked with a “No” in the respective column.

The relevance of the concomitant therapies to the evaluation of PK will be decided no later than at the RPM/DBLM.

7.3 TREATMENT COMPLIANCE

Section 4.3 of the CTP: *Compliance will be assured by administration of all trial medication in the study centre under supervision of the investigating physician or a designee. The measured plasma concentrations and/or urinary excretion of the trial medication will provide additional confirmation of compliance.*

It is not intended to list the compliance separately. Any deviations from complete intake will be addressed in the RPM/DBLM (cf. TSAP [Section 6.2](#)) and described in the CTR.

7.4 PRIMARY ENDPOINTS

Part I:

Refer to TSAP [Section 7.8](#) for a description of the analysis of safety and tolerability of BI 706321 (primary endpoint of Part I).

Part II:

Section 7.2 of the CTP: *The relative bioavailability of BI 706321 tablets compared with BI 706321 capsules, as well as the food effect comparison on tablets, will be estimated by the ratios of the geometric means (Test 1/Reference; Test 2/Test 1), and their corresponding 2-sided 90% confidence intervals (CIs) will be provided.*

Section 7.3.1 of the CTP: The primary endpoints (refer to [Section 5.1](#)) will be calculated according to the BI Standard Operating Procedure (SOP) 'Standards and processes for analyses performed within Clinical Pharmacokinetics/ Pharmacodynamics' (001-MCS-30-476) ([5](#)).

The statistical model used for the analysis of the primary endpoints will be an analysis of variance (ANOVA) model on the logarithmic scale. That is, the PK endpoints will be log-transformed (natural logarithm) prior to fitting the ANOVA model. This model will include effects accounting for the following sources of variation: sequence, subjects within sequences, period and treatment. The effect 'subject within sequences' will be considered as random, whereas the other effects will be considered as fixed. The model is described by the following equation:

$$y_{ijkm} = \mu + \zeta_i + s_{im} + \pi_j + \tau_k + e_{ijkm}, \text{ where}$$

y_{ijkm} = logarithm of response measured on subject m in sequence i receiving treatment k in period j ,

μ = the overall mean,

ζ_i = the i^{th} sequence effect, $i = 1, 2$

s_{im} = the effect associated with the m^{th} subject in the i^{th} sequence, $m = 1, 2, \dots, n_i$

π_j = the j^{th} period effect, $j = 1, 2$

τ_k = the k^{th} treatment effect, $k = 1, 2$,

e_{ijkm} = the random error associated with the m^{th} subject in sequence i who received treatment k in period j .

where $s_{im} \sim N(0, \sigma_B^2)$ i. i. d. , $e_{ijkm} \sim N(0, \sigma_w^2)$ i.i.d. and s_{im} , e_{ijkm} are independent random variables.

Point estimates for the ratios of the geometric means (test/reference) for the primary endpoints and their two-sided 90% confidence intervals (CIs) will be provided.

For each endpoint, the difference between the expected means for $\log(T)$ - $\log(R)$ will be estimated by the difference in the corresponding adjusted means (Least Squares Means). Additionally their two-sided 90% confidence intervals will be calculated based on the residual error from the ANOVA and quantiles from the t-distribution. These quantities will then be back-transformed to the original scale to provide the point estimate and 90% CIs for each endpoint.

In addition to the model-based approach all parameters will be calculated and analysed descriptively.

7.5 SECONDARY ENDPOINTS

7.5.1 Key secondary endpoints

This section is not applicable as no key secondary endpoints have been specified in the protocol.

7.5.2 Secondary endpoints

Section 7.3.2 of the CTP:

[figure not shown]
Primary analyses

[figure not shown]
[figure not shown]
Part I:

[figure not shown]
The secondary endpoints (refer to [Section 5.2.2](#)) will be analysed descriptively. Analyses will be performed for the parent drug.

Part II:

The PK endpoint $AUC_{0-\infty}$ will be assessed statistically using the same methods as described for the primary endpoint in part II.

7.7 EXTENT OF EXPOSURE

Descriptive statistics are planned for this section of the report based on the TS. The date and time of drug administration will be listed for each subject.

7.8 SAFETY ANALYSIS

All safety analyses will be performed on the TS.

If not stated otherwise, the safety results will be sorted by treatment group (Part I) / treatment sequence (Part II).

The safety data for treated subjects who failed to complete the study (dropouts or withdrawals) will be reported as far as their data are available. All withdrawals will be documented and the reason for withdrawal recorded.

7.8.1 Adverse events

AEs will be coded with the most recent version of MedDRA.

The analyses of AEs will be descriptive in nature and will be based on BI standards as presented in the corporate guideline: “Analysis and Presentation of Adverse Event Data from Clinical Trials” [BI-KMED-BDS-HTG-0041] ([7](#)).

The standard AE analyses will be based on the number of subjects with AEs (and not on the number of AEs).

No collapsing and condensing of adverse event episodes is planned.

For further details on summarization of AE data, please refer to [001-MCG-156] ([7](#)).

According to the clinical study protocol, adverse events of special interest (AESI) will be analysed:

Section 5.2.5.1.4 of the CTP: *The following are considered as AESIs:*

- **Hepatic injury**

A hepatic injury is defined by the following alterations of hepatic laboratory parameters:

- *an elevation of AST (aspartate aminotransferase) and/or ALT (alanine aminotransferase) ≥ 3 -fold ULN combined with an elevation of total bilirubin ≥ 2 -fold ULN measured in the same blood sample, or*
- *Aminotransferase (ALT, and/or AST) elevations ≥ 10 fold ULN*

These lab findings constitute a hepatic injury alert, and the subjects showing these lab abnormalities need to be followed up according to the 'DILI checklist' provided in the ISF. In case of clinical symptoms of hepatic injury (icterus, unexplained encephalopathy, unexplained coagulopathy, right upper quadrant abdominal pain, etc.) without lab results (ALT, AST, total bilirubin) available, the Investigator should make sure that these parameters are analysed, if necessary in an unscheduled blood test. Should the results meet the criteria of hepatic injury alert, the procedures described in the DILI checklist should be followed.

The analysis of adverse events will be based on the concept of treatment emergent adverse events. That means that all AEs will be assigned to screening or on-treatment phases as defined in [Section 6.1](#). AEs will be analysed based on actual treatments, as defined in [Table 6.1: 1](#) and [Table 6.1: 2](#).

Section 1.2.2 of the CTP: *The Residual Effect Period (REP) is the period after the last dose with measurable drug levels and/or pharmacodynamic effects still likely to be present. For BI 706321, a residual effect period has been determined at 8 days based on Part I. In Part I, the conservatively, a minimum observation period of 2 weeks has been selected, i.e. the individual subject's end of trial is on day 15 following dosing at the earliest (see CTP Flow Chart). In Part II it is at 8 days.*

Nevertheless, all AEs reported between administration of BI 706321 and the individual subject's end of trial will be counted as on-treatment AEs.

According to ICH E3 (8), in addition to Deaths and Serious Adverse Events, 'other significant' AEs need to be listed in the clinical trial report. These will be any non-serious adverse event that led to an action taken with study drug (e.g. discontinuation or dose reduced or interrupted).

An overall summary of adverse events will be presented.

The frequency of subjects with AEs will be summarised by treatment, primary system organ class and PT. Separate tables will be provided for subjects with SAEs, for subjects with drug-related AEs, for subjects with drug-related serious AEs, for subjects with AESIs and for

subjects with AEs leading to treatment discontinuation. In addition, the frequency of subjects with AEs will be summarised by treatment, worst intensity, primary system organ class (SOC) and preferred term (PT).

The system organ classes will be sorted by frequency, PTs will be sorted by frequency (within SOC). The MedDRA version number will be displayed as a footnote in the respective output.

In addition, frequencies of subjects with non-serious AEs that had an incidence of > 5% for at least one treatment will be summarised by treatment, primary SOC and PT.

For disclosure of adverse events on EudraCT additional information not included in a standard AE analysis will be performed. The following three entries will be created:

- Adverse Events per arm for disclosure on EudraCT
- Non-serious Adverse Events for disclosure on EudraCT
- Serious Adverse Events for disclosure on EudraCT

